1.0 Background

Chronic hyperglycemia worsens both microvascular and macrovascular complications for patients with T1DM¹,². After acute diabetes complications, cardiovascular disease (CVD) is the leading cause of death for adult T1DM patients³, making the prevention of chronic hyperglycemia critically important. Carbohydrate quantity and type affect post-prandial glycemia more than any other dietary factor in non-diabetic populations⁴,⁵. Additionally, consuming larger meals is associated with underestimation of carbohydrate quantity and mealtime insulin dose, leading to increased glucose variability⁵. These findings serve as the theoretical basis for implementing a carbohydrate restricted diet to improve HbA¹c and decrease glycemic variability. Current dietary recommendations from the ADA for patients with T1DM⁶ align with guidelines from the Institute of Medicine for healthful eating in the general population³. While the ADA recommends individualization of dietary plans for patients with T1DM, most recent guidelines state that "evidence is inconclusive for an ideal amount of carbohydrate intake for people with diabetes"⁶.

While LCDs have been associated with improved HbA1c in adults with T1DM, no randomized, prospective studies have evaluated the effect of a LCD on outcomes in the pediatric T1DM population. Cross sectional and prospective studies in adults with T1DM have demonstrated improvement in HbA1c after a LCD8-11, but these studies have significant limitations including small sample size⁹ and methodologic flaws such as using HbA1c as both a dietary adherence marker and outcome measure¹⁰. Large observational¹² and survey studies¹³ have revealed associations between lower carbohydrate intake and lower HbA1c in pediatric patients with T1DM. However, existing studies have major limitations, including significant selection bias and methodologic concerns, such as recruiting highly motivated participants from a social media group and using self-reported HbA1c as the primary outcome¹³. No study to date has prospectively investigated the impact of a LCD intervention on glycemic control in children with T1DM in a randomized controlled design. To fill this knowledge gap, in Aim 1 we will test the hypothesis that a LCD intervention will improve HbA1c compared to a SCD in pediatric patients with type 1 diabetes.

Carbohydrate quantity and type affect post-prandial glycemia while also influencing low-density lipoprotein cholesterol (LDL-C)¹⁴. Epidemiologic evidence suggests that LDL-C above 100 mg/dL is associated with increased cardiovascular disease (CVD) risk in patients with T1DM¹⁵. One study surveyed a social media group of pediatric T1DM patients who consumed a very low-carbohydrate diet (VLCD) and found glycemic control was excellent (HbA1c = 5.7%), but total cholesterol and LDL-C were elevated¹³. These findings contrast with larger studies showing that LCD reduced LCL-C in adult populations of both non-diabetic and diabetic patients¹⁶. Further, experts have noted that directly measuring the number and size of LDL particles (LCL-P) using nuclear magnetic resonance (NMR) may better capture CVD risk¹⁷ as suggested by multiple cross sectional¹⁸ and prospective studies ¹⁹⁻²². In one prospective, parallel isocaloric nutrition study in overweight men, the percent dietary carbohydrate consumption was directly proportional to smaller (i.e. worse) LDL-P size²³. No study has yet prospectively investigated the influence of a LCD on lipid profiles in

children with T1DM. In Aim 2, we will use NMR spectroscopy to comprehensively quantitate the atherogenic lipoprotein load by measuring lipoprotein particle number and size in addition to lipoprotein cholesterol concentrations.

Dietary intake influences several life domains that may affect QOL, including social interactions, personal satiety, economic, physical, and psychological domains²⁴. Significant challenges in prospective dietary intervention trials include high rates of attrition and difficulty maintaining participant compliance²⁵, both of which are ultimately linked to the impact of the diet on QOL. While improved QOL with LCD interventions has been demonstrated in patient populations including obese adults²⁴ and children with epilepsy²⁶, findings are often confounded by improvements in the underlying disease process such as weight loss or improvement in seizure frequency, respectively. No study has prospectively evaluated the impact of a LCD intervention on QOL outcomes in pediatric T1DM, which will be investigated in aim 3.

2.0 Rationale and Specific Aims

We hypothesize that pediatric patients with T1DM who consume a LCD will have improved HbA1c compared with T1DM patients who consume a standard-carbohydrate diet (SCD). We further hypothesize that differences in lipidemia and quality of life (QOL) between the groups will be minimal. To test our hypotheses, we will employ a pragmatic nutrition education intervention. The study will randomize adolescent patients (ages 13-21 years) to one of three groups (n = 15per group). We will instruct participants to consume a LCD (group 1) or a SCD (group 2), or provide no specific recommendations regarding diet (group 3). We will prescribe isocaloric diets for groups 1 and 2 equaling the estimated energy requirements of the Institute of Medicine⁷. Participants on the SCD intervention will consume 45-65% of total daily caloric intake from carbohydrates, 25-35% from fat and 10-30% from protein. Participants on the LCD intervention will consume 25-35% of total daily intake from carbohydrates, 45-65% from fat and 10-30% from protein. Group 3 will serve as a control that receives the same number of education sessions as groups 1 and 2 to teach general diabetes management but without specific dietary recommendations. This study design will allow for discrimination of the effect of the composition of the diet versus the effect of receiving any nutritional prescription.

Nutrition interventions are effective in producing dietary behavior change among adolescents²⁷, particularly when information and communication technologies (ICT) are incorporated²⁸. Previous brief nutrition interventions teaching LCD or low glycemic index diets in T1DM patients have resulted in appropriate dietary adherence^{29,30}. We will provide both traditional and ICT-based education and monitor dietary adherence with a smart-phone based nutritional tracking tool.

Aim 1 will provide preliminary estimates of improvement HbA1c after a nutrition intervention that teaches a LCD versus education reinforcing a SCD to families of pediatric T1DM patients. To determine the primary outcome—change in HbA1c—we will obtain HbA1c at baseline and at 12 weeks after the nutrition intervention. Additionally, we will quantify glycemic variability using continuous glucose monitoring (CGM) as a secondary outcome. Low rates of severe hypoglycemia, diabetic

ketoacidosis and growth attenuation have been reported in pediatric T1DM patients on a VLCD¹³, therefore, we anticipate low rates of these adverse events with the LCD intervention.

Aim 2 will provide preliminary estimates of the change in the atherogenic lipoprotein profile in patients on a LCD versus SCD. The primary outcome measure will be change in total LDL-P from baseline to 12 weeks after the nutrition intervention. As secondary outcomes, we will measure the change in other contributors to atherogenic lipoprotein load, such as high-density lipoprotein particle (HDL-P) number, small LDL-P number, and LDL size.

Aim 3 will provide preliminary estimates of the change in QOL in patients on a LCD versus SCD. Participants will complete the PedsQL, a validated QOL measure in T1DM patients, and Problem Areas in Diabetes-Teen (PAID-T), a validated measure of diabetes-specific distress, at baseline (week 0) and at 12 weeks after the nutrition intervention^{31,32}. Additionally, parents of participants will complete the WHO-5 Well-Being Index, a questionnaire for assessing subjective psychological well-being³³, and Problem Areas in Diabetes-Parent Revised version (PAID-PR), a validated measure of perceived parental burden associated with caring for a child with diabetes.³⁴

We will perform an independent samples t-test to compare outcomes between groups, in addition to multilinear regression analysis to account for potentially confounding covariates, such as total daily dose of insulin, weight change, glycemic variability as measured by continuous glucose monitoring (CGM), and age.

This proposed research will be the first prospective study to determine the effect of a LCD intervention on key diabetes outcomes in a pediatric T1DM population. This study will also provide a basis of training for a new pediatric investigator in the conduct of clinical trials under the mentorship of a highly successful mentorship team including [name] and [name].

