10.0 Statistical Considerations

10.1 Recruitment and Sample Size Justification

We have targeted an accrual of 40 participants in this pilot study to achieve two goals. First, we require a sufficient number of participants to estimate the effect size and variance of the LCD as a means to reduce HbA1c in T1DM in a future definitive trial. We utilized the method of Whitehead et al. to estimate our pilot study's optimum accrual, which proposes stepped increases in sample size based on the anticipated standard difference, d, between interventions 41,42 . We defined the minimum important difference (MID) in Δ HbA1c between LCD and SCD interventions as 0.3% and estimated a pooled SD of 0.8% based on our literature review9. If d=MID/SDpooled=0.3%/0.8%=0.38, a sample size of 20 participants per arm will optimize future sample size calculations for the definitive study, while allowing for up to 40% dropout. Second, this sample size allows for up to 4 degrees of freedom in multivariable linear regression analysis.

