10.2 Statistical Analysis

Statistical analysis will be performed using an independent samples t-test to compare change from baseline to 3 months post-intervention values from each aim (Δ HbA1c, Δ LDL-P, and Δ QOL score) between the two groups. We will also perform a series of multivariable linear regression analyses with change in primary outcomes from each aim (Δ HbA1c, Δ LDL-P, and Δ QOL score) from baseline to 12 weeks post-intervention as the dependent variable. Explanatory variables in the multivariable linear regression modeling will include mean total daily dose of insulin normalized for body mass, weight change, coefficient of variation of glucose as measured by CGM, and age.

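### Aims 2 and 3 hypothesise minimal lipid and QOL differences, but the only planned between-group test is a t-test of difference, which cannot support that hypothesis

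*Combined protocol and SAP*

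**What the plan says.** Section 2.0 sets two kinds of hypothesis. For HbA1c it expects the low-carbohydrate diet (LCD) to do better than the standard-carbohydrate diet (SCD). For the other outcomes it expects little or no difference: "We further hypothesize that differences in lipidemia and quality of life (QOL) between the groups will be minimal". The next sentence opens the design description with "To test our hypotheses, we will employ a pragmatic nutrition education intervention", so both are presented as hypotheses to be tested.

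The analysis does not distinguish them. Section 2.0 says "We will perform an independent samples t-test to compare outcomes between groups". Section 10.2 applies an "independent samples t-test to compare change from baseline to 3 months post-intervention values from each aim", naming the changes in HbA1c, LDL-P and QOL score together. A multivariable regression follows; its listed explanatory variables are insulin dose per body mass, weight change, CGM coefficient of variation and age. Group is not listed.

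Section 10.1 defines an important difference and an SD for HbA1c only ("between LCD and SCD interventions as 0.3"%; "estimated a pooled SD of 0.8% based on our literature review"). There is no equivalence or non-inferiority margin, no confidence-interval rule, no alpha, and no SD or important difference for LDL-P or QOL.

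In mitigation, section 2.0 describes Aims 2 and 3 as giving preliminary estimates, and section 10.1 calls the study a pilot.

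**The concern.** A t-test of equality suits Aim 1, where a difference is expected. For Aims 2 and 3 the hypothesis lies on the other side: the test can count against it by rejecting equality, but cannot count for it. Failing to reject may mean the difference is small, or only that the data are too few to show it.

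The sample size then works the wrong way. The fewer the completers, the more likely p>0.05, and the more the result can look like agreement with the hypothesis.

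LDL-P and QOL bear on whether the diet is acceptable as well as effective. The background section reports raised total cholesterol and LDL-C in a survey of children on a very low-carbohydrate diet, and links QOL to attrition and compliance. A conclusion of no meaningful difference that the data cannot carry could pass into the planning of the definitive trial.

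**Working it through.** **The plan's own figures.** Section 10.1: d = 0.3/0.8 = 0.375, given as 0.38. This reproduces. 20 per arm in two arms is 40, and 20 × (1 − 0.40) = 12 completers. The 20 itself comes from a stepped pilot-size rule whose table is not in the documents, so it can be neither reproduced nor refuted. No power is stated for any aim, so Aims 2 and 3 have no figure to reproduce.

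**Inputs.**
- Per arm: 15 (sections 2.0 and 6.1.1.6) or 20 (section 10.1). These conflict, so both are carried through.
- Dropout: up to 40% (section 10.1), giving 15 × 0.6 = 9 and 20 × 0.6 = 12.
- Alpha: not stated; two-sided 5% assumed.
- Scale: SD units, because no SD is given for change in LDL-P or QOL.
- True difference: not given; 0.375, 0.5, 0.8 and 1.0 SD are shown as assumptions.

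**Step 1: chance of a non-significant t-test when a difference exists.** With n per arm, degrees of freedom are 2n − 2 and the noncentrality is d × √(n/2). The probability sought is that |t| falls below the two-sided 5% critical value. Example: n = 15, d = 0.5 gives 28 degrees of freedom, critical value 2.048, noncentrality 0.5 × √7.5 = 1.369, and probability 0.738.

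| Completers per arm | 0.375 SD | 0.5 SD | 0.8 SD | 1.0 SD |
|---|---|---|---|---|
| 9 (15 less 40%) | 88% | 83% | 64% | 49% |
| 12 (20 less 40%) | 86% | 78% | 53% | 35% |
| 15 | 83% | 74% | 44% | 25% |
| 20 | 79% | 66% | 31% | 13% |

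**Step 2: what an observed difference of zero would leave open.** The 95% CI half-width in SD units is t(0.975, 2n − 2) × √(2/n).
- n = 9: 2.120 × 0.4714 = 1.00
- n = 12: 2.074 × 0.4082 = 0.85
- n = 15: 2.048 × 0.3651 = 0.75
- n = 20: 2.024 × 0.3162 = 0.64

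Differences up to these values, in either direction, would stay inside the interval; larger ones would be excluded.

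**Step 3: could a margin rule rescue the hypothesis at this size?** Take two one-sided 5% tests, a true difference of zero and 80% power. The approximate n per arm is 2 × ((1.645 + 1.282)/margin)². For a 0.5 SD margin this is 2 × (5.854)² = 68.5, so 69 evaluable per arm; for 0.8 SD it is 27. Simulated power with a 0.5 SD margin is about 0.2%, 0.5% and 3% at 12, 15 and 20 per arm. With 0.8 SD it is about 22%, 38% and 60%. These margins are illustrative.

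**The case against.** The strongest reply is that this is a pilot, Aims 2 and 3 are already worded as preliminary estimates, and running a t-test does not prevent anyone from reporting the difference with an interval. On that view only one hypothesis sentence is out of step. This stands in part, and it lowers the seriousness of the point. It does not remove the mismatch: the same section says the hypotheses will be tested, and section 10.2 specifies a test but no interval.

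A reader might infer that the sponsor will take p>0.05 as confirmation that the diet leaves lipids and QOL unharmed. No section says how a non-significant result will be read. The documents leave that reading open but do not state it.

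A reader might also infer that non-significance is likely whatever the true difference. That is too strong. It holds at 0.5 SD for all four sample sizes. At 0.8 SD the chance is 44% with 15 and 31% with 20 completers per arm, and exceeds one half only after heavy dropout. At 1.0 SD it is below one half throughout. The 0.5 SD benchmark is an assumption, not a figure from the plan.

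Finally, lipids and QOL are not among the risks listed in section 7.1. Treating them as harm and acceptability outcomes rests on the background section.

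**Conclusion.** The point holds as a mismatch between hypothesis and test. A t-test of difference cannot support the minimal-difference hypothesis in section 2.0, and the plan supplies neither an interval nor a margin that could. This needs no assumption about effect size or sample size.

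The practical size does depend on assumptions: two-sided 5%, SD units, and the sample sizes the documents allow. A true 0.5 SD difference would be missed 66% to 83% of the time, a 0.8 SD difference 31% to 64%. The conclusion is the same whether 15 or 20 per arm is right, though those two figures need reconciling. The pilot status makes this something that should be corrected, not a fatal flaw. That a null result would be misread remains an inference.

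**What to change.** 1. In section 10.2, make the LCD-SCD difference in change, with its 95% CI, the reported result for LDL-P and QOL. Take it from a model with a group term and baseline covariates only: the baseline value of the outcome and age. With group, that is three terms, within the four degrees of freedom section 10.1 allows. Leave weight change, and insulin dose or CGM variability measured after randomisation, out of this model. The diet can alter them, so adjusting for them could remove part of its effect.
2. State in section 10.2 that p>0.05 will not be taken as support for a minimal difference.
3. In section 2.0, reword the lipid and QOL hypothesis as estimation, matching the wording already used for Aims 2 and 3.

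An equivalence margin is not recommended as the main remedy, because at these sample sizes a margin of 0.5 SD or less could almost never be met.

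The cost is a change of wording and one respecified model, with no added participants, visits or measurements. The downside is that the pilot can no longer claim to confirm minimal lipid or QOL differences.

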3.0 Animal Studies and Previous Human Studies

3.1 Previous Human Studies – Adult T1DM Population

A recent systematic review described eight studies that investigated the effect of a low-carbohydrate diet on glycemic control using HbA1c as the primary outcome. Of these studies, four reported non-significant changes in HbA1c with a LCD while three reported statistically significant reductions⁸.

3.2 Previous Human Studies – Pediatric T1DM Population

Published studies focused on the effects of a low carbohydrate diet on outcomes in pediatric T1DM have been limited to observational and survey studies.

One study surveyed an online social media group of pediatric T1DM patients who consumed a very low-carbohydrate diet (VLCD) with an average carbohydrate intake goal of 36 +/- 15 grams of carbohydrates per day and found glycemic control was excellent with a reported mean

HbA1c of $5.7\%^{13}$. There were low rages of adverse events, including episodes of diabetic ketoacidosis (1%), hypoglycemia with seizure or coma (2%), hypoglycemia requiring assistance from others (12%), and hypoglycemia requiring glucagon (4%)¹³.

A large cross-sectional observational study in 46,010 patients with T1DM aged 1-18 years in Germany and Austria found that lower carbohydrate intake was associated with lower HbA1c (p < 0.001) with the average HbA1c being 0.2% lower in the lowest quartile of carbohydrate intake than in the highest quartile 12 .

4.0 Inclusion/Exclusion Criteria

Table 1: Inclusion and Exclusion Criteria

5.0 Enrollment/Randomization

5.1 Recruitment

5.1.1 Recruitment Resources

We will use multiple tools to identify prospective study participants. The PI will contact intramural and extramural endocrinology colleagues at Vanderbilt and in the region to discuss this study and ask them to refer potential subjects. The

Vanderbilt Eskind Diabetes Clinic is a large academic center that sees approximately 2,700 patients with T1DM annually. The study team will also use additional research tools including Research match, Subject locator, and My Research at Vanderbilt. We will post flyers and send an institution-wide mass email through the Research Notifications Distribution List. In addition, we will post our research flyer on social media platforms (e.g. Facebook and Twitter) to target further potential T1DM and control group participants. For example, the Middle TN JDRF Chapter Facebook page has a large number of followers across the state of Tennessee many of whom may participate in our research.

Participants will also be recruited from the Vanderbilt Children's Endocrinology Franklin

IRB-approved flyers will be posted in the clinic (both provider workroom and in patient care areas). I will also ask my endocrinology colleagues at Vanderbilt who see patients at the Franklin clinic to refer potential subjects.

5.1.2 Initial Contact with Potential Participants

[figure not shown]
Once the research team becomes aware of a potential subject, we will either telephone the participant (or parents in the case of potential pediatric participants) or visit with them in person during an endocrinology clinic visit. The initial discussion will aim to make a preliminary assessment of whether the subject might be eligible to participate in the study. Study personnel will ask the potential subject to share his or her:

- Diagnosis of T1DM
- Age
- Weight
- Height
- Most recent HbA1c
- Diabetes duration
- Medications
- History of severe hypoglycemia in the past 12 months
- History of any episodes of DKA in the past 12 months
- Food preferences and restrictions
- Level of physical activity
- Use of insulin pump and CGM
- Ability to read and speak English

Inclusion and exclusion criteria are listed in table 1. We will invite eligible subjects to participate in the initial screening visit. The initial screening visit will occur in the Vanderbilt Eskind Diabetes Center or Vanderbilt Children's Endocrinology Franklin clinic. The participant will receive an electronic or paper copy of the informed consent document to review prior to the initial screening visit.

5.2 Enrollment

A member of the study team (i.e. key study personnel, KSP) will obtain written, informed consent or adolescent ascent with parental consent at the beginning of the screening visit as detailed in section 6.1.1.1. Once consent/assent is obtained, the participant will be enrolled in the study. A detailed description of special protection for adolescents as research subjects follows in section 7.2 below.

The performance site at the Vanderbilt Children's Endocrinology Franklin clinic is not engaged in research. KSP from this study would utilize the clinic space to meet with participants for study visits. Phlebotomists at this location would be utilized to obtain blood work, which would then be handled by KSP.

5.3 Randomization

Random permuted blocks with a fixed size of 3 will be used for randomization into treatment groups. We will stratify participants based on open vs. closed loop insulin pump use and age prior to randomization.

5.4 Participant Compensation

Research subjects will be compensated for their time and inconvenience in the study in the form money in the amounts specified below. Following study completion, participants will be mailed a check equal to the dollar amount below.

- Visit 1 (Screening visit): the initial screening visit will last approximately 2-3 hours. Subjects who complete their screening visit will be compensated \$25.
- Visit 2 (Week 1 visit): this visit will last approximately 2-3 hours. Subjects who complete this week 1 visit will be compensated \$25.
- Visit 3 (Week 12 visit): this visit will last approximately 1-2 hours. Subjects who complete this week 12 visit will be compensated \$25.
- Telephone visits (weeks 2, 4, 8): these visits will last approximately 30-60 minutes. Subjects who complete these visits will be compensated \$10 per visit.
- Participants will receive full compensation for study visits and telephone visits only if they have completed all pre-visit tasks, which will be outlined in both the consent documentation and included in the written instructions participants are given in the preceding visit.

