6.1.1.6 Randomization

We will then randomize patients to 1 of 3 groups: group 1 is low carbohydrate diet, group 2 is standard carbohydrate diet, group 3 is general diabetes education without dietary recommendation. Each group will contain 15 participants. Random permuted blocks with a fixed size of 3 will be used for randomization into treatment groups.

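### A printed, fixed block size of 3 for three equal, visible arms lets anyone who tracks earlier allocations know about 27% to 33% of the next ones with certainty

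*Combined protocol and SAP*

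**What the plan says.** Section 5.3 of the combined protocol and SAP sets the allocation rule: "Random permuted blocks with a fixed size of 3 will be used for randomization into treatment groups". Section 6.1.1.6 repeats it, names the three groups ("We will then randomize patients to 1 of 3 groups: group 1 is low carbohydrate diet, group 2 is standard carbohydrate diet", with general diabetes education as the third) and sets equal sizes: "Each group will contain 15 participants". Section 5.3 adds stratification: "We will stratify participants based on open vs. closed loop insulin pump use and age prior to randomization". It gives no age cut-points, so the number of strata is not known.

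Other sections show what is known, and when:

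- **Before invitation (5.1.2).** The research team makes the approach: "Once the research team becomes aware of a potential subject, we will either telephone the participant". Its questions cover most recent HbA1c, age, pump and CGM use, activity and "Food preferences and restrictions".
- **Screening visit (5.2, 6.1.1).** A study team member takes consent at the start of the visit. Randomization is the last procedure listed for that visit.
- **After randomization (6.1.2, 6.1.5).** Groups 1 and 2 track nutrition in the app, while group 3 keeps a glucose and exercise log. At telephone visits the study team reinforces the assigned diet.

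The documents do not describe who generates the sequence, who holds it, how an allocation is released, or any blinding of the study team.

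**The concern.** When the block size equals the number of arms, every complete block ends with an allocation that can be deduced. The usual protection, a concealed list, does not help: the last allocation is worked out from the two already seen, not from the list. Stratification does not help either if the team already knows the next person's pump type and age, and 5.1.2 has it ask for both before any invitation.

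At stake is the comparability of the groups. Response to a taught diet plausibly depends on motivation and food habits, and the team learns something of these at first contact. If knowledge of the next arm influenced which adolescent was approached, or when, the groups could differ in expected HbA1c change for reasons unrelated to diet. The analysis in 10.2 would not reliably remove this. The t-test is unadjusted, and the listed regression covariates (insulin dose, weight change, glucose variability and age) include neither baseline HbA1c nor any measure of motivation. Because the pilot is meant to supply the effect size for a definitive trial, a distorted estimate would carry forward.

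**Working it through.** The plan states no predictability figure, so there is none to reproduce.

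**Inputs from the documents**
- Block size 3, fixed (5.3 and 6.1.1.6).
- Three equal arms of 15, so 3 × 15 = 45 (6.1.1.6). Section 10.1 instead says "We have targeted an accrual of 40 participants in this pilot study to achieve two goals", so 40 is checked as well.
- Two pump-type levels crossed with an unstated number of age levels (5.3).

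**Assumptions**
- Blocks run within strata, which 5.3 implies but does not spell out.
- Stratum sizes of 11 and 15 are used for illustration. Four equal strata of 45 hold about 11 each. A stratum of 15 is five complete blocks and so gives the upper end. One to six strata are also checked.
- An observer records earlier allocations by stratum and knows the possible block sizes.

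**One complete block of 3**
- The chance of guessing the arm is 1/3 at position 1, 1/2 at position 2 and 1 at position 3.
- Certain allocations: 1/3 = 33.3%.
- Best-guess success: (1/3 + 1/2 + 1)/3 = 61.1%, against 33.3% by chance.

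**Stratum of 15 (five complete blocks)**
- Certain: 5/15 = 33.3%. Best guess: 61.1%.

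**Stratum of 11 (three complete blocks plus two places)**
- Certain: 3/11 = 27.3%.
- Best guess: [3 × (1/3 + 1/2 + 1) + 1/3 + 1/2]/11 = (5.5 + 0.833)/11 = 57.6%.

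**Number of strata (simulation with random stratum sizes): certain share under fixed blocks of 3**

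| Total | 1 stratum | 2 | 4 | 6 |
|---|---|---|---|---|
| 45 | 33% | 32% | 30% | 29% |
| 40 | 32.5% | 32% | 30% | 28% |

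At 45 participants this is about 13 (0.289 × 45) to 15 (0.333 × 45) people.

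**Alternatives (strata of 11 to 15, possible sizes equally likely, observer knows which sizes are possible)**

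| Block rule | Certain | Best guess | Largest imbalance between two arms from an unfinished block |
|---|---|---|---|
| Fixed 3 | 27% to 33% | 58% to 61% | 1 |
| Random 3 and 6 | 6% to 8% | 54% to 57% | 2 |
| Random 3, 6 and 9 | 2% to 3% | 52% to 54% | 3 |

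Certain allocations fall about fourfold with sizes 3 and 6 (for a stratum of 15, 33% to 8%). Best-guess success falls by about 4 points (61% to 57%, or 58% to 54%).

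The documents give nothing from which to turn these rates into a bias in HbA1c, so no such figure is offered.

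**The case against.** **Roles are not spelled out.** A reader might infer that one small team recruits, consents, randomizes and teaches, and so always knows the next arm. The documents do not say this. Outside endocrinologists may refer patients (5.1.1), consent is taken by the investigator or designated personnel (6.1.1.1), and some key personnel do not teach (6.1.3.7). Nor do they say that recruiters track allocations. This stands: the figures apply to someone who does track them.

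**No bias is shown.** A reader might also infer that the HbA1c comparison is biased. The documents support only an opportunity. The outcome is a laboratory value, the trial seeks preliminary estimates, and consent already precedes randomization. Timing is limited too, since visit 2 is tied to a routine clinic visit (6.1.3) and the next participant must fall in the relevant stratum. These points limit the stakes. They do not remove discretion over whom to invite, which comes before consent.

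**The remedy is partial.** Selection can act on a good guess as well as on a certainty. The excess over chance falls only from about 26 to 22 points (59% to 55% against 33%, at 45 participants in four strata). This stands, and it is why release control belongs in the fix alongside block size.

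**Small blocks protect balance.** With 40 to 45 participants over several strata, blocks of 3 keep each stratum within 1, and larger imbalances could add up across strata. This is a real trade-off, but a small one.

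**Conclusion.** The point holds as an avoidable weakness in allocation. With a known fixed block of 3 and visible arms, about 27% to 33% of allocations are certain to anyone who follows the sequence within strata, and the best guess succeeds 58% to 61% of the time against 33% by chance. The certain share changes little over one to six strata and totals of 40 or 45 (28% to 33%). It rests on blocks running within strata and on someone tracking allocations, neither of which the documents state outright.

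The conclusion is that selection bias is possible, not that it will occur or how large it would be in HbA1c. How the sequence is generated and released is undescribed, which is not evidence that it is handled badly. The point merits action because the change is cheap and because a hidden list alone would not solve it.

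**What to change.** - In 5.3 and 6.1.1.6, replace the fixed size of 3 with randomly varying block sizes that are multiples of 3, for example 3 and 6, or 3, 6 and 9.
- Do not state the sizes to recruiting staff. Keep them out of the protocol text those staff use.
- State who generates the sequence and who releases it.
- Release each allocation through the REDCap system already planned in section 11.0, one participant at a time, and only after consent and eligibility are recorded. Consent before randomization is already the stated order; the recorded lock and controlled release are what would be new.

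The cost is a new randomization list, a few lines of text and some REDCap set-up. The statistical price is that an unfinished block can leave an imbalance of 2 per stratum (3 if blocks of 9 are used) instead of 1. With strata this small, sizes 3 and 6 are the more cautious choice for balance, and adding 9 gives the lower predictability. Neither makes allocation unpredictable to a determined guesser.
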